8.3.2 Quantitative data collection

Quantitative data on acceptability and feasibility will be collected from among all healthcare workers who are working on IVON-PP trial across all sites. We will use the Acceptability of Intervention Measure (AIM) and Feasibility of Intervention Measure (FIM) tools developed by Weiner et al. Data will be collected electronically using RedCap to generate a link to the self-administered survey tools that will be send to study participants. survey.

8.4 Ethical issues and protection

We expect that participating in interviews in this study will expose participants to minimal risk (considering that the topic in question is not of a sensitive issue) and are therefore proposing verbal consent for all FGDs and KIIs. This will also provide ease of consenting illiterate participants and groups for the FGDs. Consent script will be translated to participant's language of choice and will be administered by study staff who speak the local language within the sites and communities. Study staff will ask participants to summarize the study activities to ensure that all activities are well understood. During the consent process, any misunderstandings regarding procedures, risks, or benefits will be clarified. Individuals will be provided with information on how to contact the study staff for further clarifications. Study staff have been trained extensively on how to ensure that individuals provide voluntary informed verbal consent.

For quantitative data collection, an electronic informed consent form will accompany the tools to be filled online by willing participants (healthcare workers) before completing the survey.

8.5 Data analysis

Data obtained through audio recordings will be transcribed then analyzed using thematic analysis aided by NVivo software (QSR International, Melbourne, Australia). Data analysis will be both deductive and inductive. Deductive analysis will be guided by the CFIR. Two researchers will independently conduct the initial coding after familiarization with the transcripts, thereafter subsequent and final coding criteria will be agreed by both researchers following iterative review of emerging themes as informed by the research questions. The final sets of themes and sub-themes relevant to the overall research goals will be reported and supported with verbatim quotes.

8.5.1 Framework for triangulating methods

The RE-AIM will serve as an overarching framework for triangulating methods and findings from the clinical effectiveness trial and the implementation research (Table 6).

Table 6: Framework for triangulating methods

RE-AIM Domain	Outcomes	Measures	Data sources
Reach	Dose delivered	The proportion of targeted women who are approached/informed about the new treatment	Trial implementation data
	Dose received	The proportion of approached/ informed women who accept the treatment	Trial implementation data
Effectiveness	Clinical effectiveness	Primary outcomes	Surveys and clinical records
Adoption	Acceptability	Barriers and facilitators to adoption	FGDs/KIIs guided by the CFIR
Implementation	Feasibility	Implementation drivers/ climate (Barriers and facilitators)	Qualitative focus group discussions/ key informant interviews guided by the CFIR

8.6 Timeline of data collection for implementation research

Data collection will be collected at baseline and endline of the trial. This approach will provide preimplementation perspectives as well as collect data on potential change in perspective as the trial progresses. The timeline for both qualitative and quantitative data collection is detailed in table 7.

Table 7: Timeline of data collection

Implementation outcome	Data collection Timepoint(s)		Target stakeholders	Mode of data collection	
	Baseline	During	End of study		
Acceptability (includes facilitators and barriers)	Х		Х	Healthcare workers, pregnant women and their partners, health facility managers, state government health officials, policymakers	FGDs, KIIs AIM survey
Feasibility	X		Х	Healthcare workers	FGDs, KIIs FIM survey

9 DATA MANAGEMENT PLAN

9.1 Data collection

IVON-PP will adopt REDCap, a secure web-based application to collect all relevant study data. Electronic case report forms, surveys and other data collection instruments have been developed and refined in the REDCap to collect information at enrolment, follow-up, end of study visits and for adverse events. Other study instruments in the REDCap are the EPDS, fatigue scale, MIB scale and quality of life scale e-forms. Designated investigators and study staff will enter the information in real time as required by the protocol into these electronic forms on the REDCap and source documents as indicated. REDCap page will be accessed at: http://live.ivonpptrial.com/

A data management team consisting of a data manager, a data officer and data entry clerks will coordinate data collection and management. They will ensure real-time collection of complete, accurate and reliable data by the study staff as sites. Clinical monitors will review the e-CRFs and other tools and cross reference with source documents for completeness and accuracy and instruct site personnel to make any required corrections or additions as necessary.

9.2 Data management plan and quality control

The data management team will follow the data management plan (DMP) for the trial that specifies the methods for *data handling*, data collection, data entry, and transmission, data compilation and management, data quality and security and data analysis. (See data management plan (DMP))

The team will submit regular weekly/monthly report to the chief investigator or designee.

9.3 Data Management and analysis

The assignment of participants into analysis populations will be performed prior to database lock and any data analysis.

- Randomized all participant who receive a randomization number.
- Intention-to-treat (ITT) all randomized patients with at least one relevant post-baseline efficacy assessment, and who had at least one dose of study drug. Following the intention-to-treat principle, patients will be analyzed according to the treatment they were assigned to at randomization.
- Primary Analysis (PA) all ITT patients that completed 2- and 6-weeks postpartum visit.
- Per Protocol (PP) all PP patients that meet all the following:
 - Took at least 80% of scheduled study drug
- Safety all patients that received at least one dose of study drug and had at least one post-baseline safety assessment. Patients will be analyzed according to treatment received.

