3 OUTCOMES

3.1 Clinical outcomes

3.1.1 Primary outcome

Proportion of participants who are non-anemic at six weeks postpartum. Non-anemic state is defined as hemoglobin level ≥ 11.0 g/dl.

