4.3 Sample size

We will enroll 1400 women into the trial. Power calculations assume a 1:1 randomization ratio to each of the two treatment groups.

For the primary outcome (anemia), we used data from a recent meta-analysis (28), which reported that 39% of women were anemic at six weeks postpartum. A sample size of 697 participants per arm would

^{**}A prospective participant with chronic medical condition (e.g HIV infection) will not be excluded unless there are contra-indication for the use of iron supplementation.

provide 90% power to detect to detect a relative reduction of 20% for IV iron to reduce the event rate of anemia at six weeks postpartum to 30%, after accounting for 10% loss to follow-up.

Bearing in mind the proposed one-time interim analysis to be conducted by the Data and Safety Monitoring Board (DSMB) at mid recruitment, we applied the O'Brien-Fleming rule (29), adjusting our final alpha level to 0.0492 (*See section 9.3 for interim rule*), which increased our final sample size to 1400 (700 per arm of the study).

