4.6 Study intervention

4.6.1 Administration of study drugs

Administration of ferric carboxymaltose (FCM): Eligible women randomized to the intervention arm (FCM) will be observed at the dedicated ward or daycare room for treatment initiation and will be given intravenous ferric carboxymaltose (FCM) in a single dose of 20mg/kg up to a maximum of 1000mg. This dose will be administered as an infusion diluted in 200 ml 0.9% sodium chloride and infused over a minimum of 15 - 20 minutes (Table 2). Thereafter, they will be observed closely for a minimum of 30 minutes after infusion. [Refer to IVON-PP Trial - Protocol for the administration of Intravenous Ferric

Carboxymaltose and the Emergency Treatment of Hypersensitivity Reaction Type 1 (Anaphylaxis); Protocol no 2].

Administration of Ferrous Sulphate (FS): The women randomized to the control arm (FS) will be given for take home, one **200mg tablet of study drug, ferrous sulphate** which contains 65mg of elemental iron, to be taken two times daily and 1 hour before meals or 2 hours after meals with a full glass of water till 6 weeks postpartum (Table 2). The study drug for the control arm (FS) will be prepared in sachets, dispensed, and packaged in 2-week, 4-week and 6-week doses for the appropriate visit schedule. The women will be sent daily reminders by text messages and asked to bring in their empty sachets for sighting and for a pill count and evaluation of compliance at each study visit.

Table 2: Oral and intravenous Iron dosing for intervention and control arms

Study arm	Study medications	Dose	Comments
Intervention	Drug: intravenous ferric carboxymaltose	Single dose of 20mg/kg (to a maximum of 1000mg)	A dose of 20mg/kg body weight (but not exceeding a max of 1,000mg) of ferric carboxymaltose will be given in 200mls of normal saline as a single dose infusion administered over 15 – 20 minutes
Control	Drug: oral ferrous sulphate	One 200mg tablet (65 mg elemental iron) 2 times daily	Treat with 2 times daily regimen till six weeks postpartum. ^{a, b}

a. All patients will also receive 5mg folic acid daily and 400mg Vitamin C daily.

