4.10.3 Follow-up visits (2, 6, and 12 weeks postpartum)

• Each participant will have follow-up visits at home or healthcare facility whichever is preferred except the 6 weeks visit which as routine should be at the health care facility.

The following steps will be taken at the follow up visits:

- 1. Go to REDCap, using the participant's study ID-
 - Complete and submit the Edinburgh Postnatal Depression Scale (EPDS) e-form (Appendix xi) at 6 weeks visit.
 - Complete and submit the Maternal infant bonding scale e-form (Appendix xii) at 6 weeks visit.
 - Complete and submit the fatigue scale e-form (Appendix xiii) at 6-week visit.
 - Complete and submit the quality of life (WHOQOL BREF) scale e-forms (Appendix xiv) at 6 weeks visit.
 - Evaluate for the presence of any symptom and sign (adverse event(s) AEs)) and if any,
 complete and submit the adverse event e-form for all follow up visit.

The visit e-CRF will be available to you ONLY after completing and submitting the above steps on REDCap.

- Evaluate compliance to study drug and document in the e-CRF.
- Complete follow-up visits e-CRF (Appendix xv) and relevant source documents
- Re- supply study drug (control arm) in an amount sufficient to last until the next follow up visit up to the 6th week visit.
- Counsel and necessary referral (e.g., family planning clinic, psychosocial support etc.).

2. Additional steps

- Perform malaria rapid diagnostic test (RDT) with SD BIOLINE Malaria Ag P.f and complete the *Malaria POCT worksheet* as appropriate (2- and 6-week postpartum visits).
- Do hemoglobin concentration check with the haemoglobinometer at every follow up visit. And complete Hb check worksheet as appropriate.
- Take blood samples for laboratory tests as indicated for visit type and complete the blood sample collection log on REDCap. This sample can also be used for the hemoglobin concentration check.
- Counsel as appropriate based on any queries they might have about their health or that of their newborn/baby.

The research team at site will be responsible for the visits and attending to the participant and resupplying the participants with the study drugs at two weeks.

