6.5 Study drug discontinuation

- Study drug must be discontinued for a given participant if the investigator determines that continuing it would result in a significant safety risk for that patient. This should only be done after discussion with and approval from the chief investigator/PI.
- The following circumstances require study drug discontinuation:
 - Emergence of severe adverse reactions such as severe nausea/vomiting, allergy, severe pruritus, anaphylaxis, and other life-threatening symptoms
 - Abnormal laboratory values: Hb <6g/dl

Participants who discontinue study drug for adverse effects (AE) or any reason other than an AE will be followed to study completion at 6 months postpartum at which times all the assessments as listed for the visits will be performed. Reasons for study drug discontinuation should be completed, giving the date and primary reason for stopping the study drug under the relevant section of the CRF.

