9.4 Data analysis plan

Primary analysis will be conducted by the intention to treat principle. Categorical variables will be expressed as frequencies and percentages. For continuous variables, a Shapiro-Wilk test of normality will be performed, and normally distributed data will be presented as means ± SD, while non-normally distributed data will be presented as median and interquartile range (IQR). However, the literature will be reviewed to ensure that variables are handled in their natural form. The effect of IV iron (vs. oral iron) on the primary endpoint (anemia at six weeks post-partum) would be analyzed using log-binomial regression models to obtain relative risks, 95% confidence intervals and p-values. The extent to which inclusion of baseline covariates modifies the precision of estimates would be explored. Generalized linear mixed models will be used to estimate the effect of treatment arm on repeated measures of hemoglobin and iron status biomarkers. The proportions of participants in the treatment arms who are anemic or iron deficient, and the proportions of participants who achieve anemia correction at 6 weeks and 6 months follow-up with be compared. Kaplan Meir plots and log-rank test will be used to explore the time to anemia correction. Subgroup analysis will be conducted to compare study findings by mode of delivery (caesarean vs vaginal delivery), and by the occurrence of primary post-partum hemorrhage. Two tailed test of hypothesis and 95% confidence interval is assumed as statistical level of significance. Stata version 17 (Stata Corp, Texas, USA) statistical software will be utilized for analysis. The variance estimator with cluster option (clustering on site of study) will be utilized.

Interim analysis will be conducted after achieving half of the sample size. Based on O'Brien-Fleming method (29), the threshold for significance of the primary endpoint at the interim analysis will be alpha = 0.0054. The clinical trial is terminated if the null hypothesis is rejected. The alpha level for the analysis at the end of the study will be adjusted to 0.0492 based on alpha adjustment based on O'Brien-Fleming method.

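### Both candidate primary sets in section 9.3 can exclude randomized women whose six-week hemoglobin is known, contrary to the intention-to-treat analysis promised in section 9.4

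*Protocol*

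**What the plan says.** The primary outcome in Protocol section 3.1.1 is "Proportion of participants who are non-anemic at six weeks postpartum", so one hemoglobin value at week 6 determines it.

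Section 9.3 lists the analysis populations:

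- A Randomized set, to which no analysis is assigned.
- An ITT set: "all randomized patients with at least one relevant post-baseline efficacy assessment, and who had at least one dose of study drug". Women in it are analyzed by assigned arm.
- A Primary Analysis set: "all ITT patients that completed 2- and 6-weeks postpartum visit".
- A Per Protocol set, which is defined in terms of itself plus an 80% drug-intake rule.

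Section 9.4 says: "Primary analysis will be conducted by the intention to treat principle". It specifies a log-binomial model for six-week anemia and does not say which set the model uses.

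Three other passages bear on this. Section 6.5 says that women who stop study drug "will be followed to study completion at 6 months postpartum at which times all the assessments as listed for the visits will be performed". Section 4.6.1 says that women "randomized to the control arm (FS) will be given for take home" their tablets, while the infusion is given once under observation at the facility. Section 4.10.3 makes the site team responsible for "resupplying the participants with the study drugs at two weeks".

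**The concern.** Intention to treat means that every randomized woman counts in her assigned arm. Analyzing by assigned arm does not bring back women who have already been removed from the set.

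The dose condition and the week-2 condition both act after randomization, and neither is needed to know the primary outcome. A woman with a valid six-week hemoglobin can be lost because she took no dose. Under the Primary Analysis set she can also be lost because she missed week 2. The trial tracks women and follows them after they stop drug, so it works to collect outcomes that these definitions would discard.

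Week 2 is the resupply visit in the oral arm only, and both women and site staff know the allocation. Attendance may therefore depend on arm, and also on adherence and recovery. If it does, the retained groups are no longer the groups that randomization made comparable, while the result is still labeled intention to treat.

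**Working it through.** **Inputs from the protocol.** Section 4.3: 39% anemic at six weeks with oral iron ("reported that 39% of women were anemic at six weeks postpartum"), 30% with IV iron, 697 per arm before and 700 after the interim adjustment, 10% loss to follow-up, 90% power, final alpha 0.0492. Section 9.4: two-tailed test.

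**Assumptions, not in the documents.** m is the share of women with a known six-week hemoglobin whom the set definitions remove. r is the anemia rate among those removed.

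**Formulas.** Power = Φ[(|p1 − p2| − z·se0)/se1]. Here z is the two-sided critical value, se0 the standard error with pooled proportions, and se1 the standard error with separate proportions. The rate among retained women is (p − m·r)/(1 − m).

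**1. The plan's own figure.** 697 × 0.9 = 627 per arm. At 39% versus 30% and alpha 0.05, power is 91.9%, against 90% stated. The figure reproduces within two points.

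**2. Every woman with a six-week value analyzed.** 700 × 0.9 = 630 per arm. Power at alpha 0.0492 is 91.9%.

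**3. Equal removal, unrelated to outcome.** The retained rates are unchanged, so there is no bias and only power is lost.

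| m removed (assumed) | Per arm kept | Known outcomes discarded, both arms | Power |
|---|---|---|---|
| 0% | 630 | 0 | 91.9% |
| 2% | 617 | 25 | 91.4% |
| 5% | 598 | 63 | 90.6% |
| 10% | 567 | 126 | 89.0% |
| 15% | 536 | 189 | 87.2% |
| 20% | 504 | 252 | 85.2% |

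At this alpha, 90% power needs 587 per arm. Power therefore drops below 90% once m exceeds 1 − 587/630 = 6.8%.

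**4. Removal related to arm or outcome.** The true anemia RR is 0.30/0.39 = 0.77.

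| Removed (assumed) | r (assumed) | Oral rate kept | IV rate kept | Apparent RR |
|---|---|---|---|---|
| 10% oral, 0% IV | 50% | (0.39 − 0.05)/0.90 = 37.8% | 30.0% | 0.79 |
| 10% oral, 0% IV | 60% | (0.39 − 0.06)/0.90 = 36.7% | 30.0% | 0.82 |
| 15% oral, 5% IV | 60% | (0.39 − 0.09)/0.85 = 35.3% | (0.30 − 0.03)/0.95 = 28.4% | 0.81 |
| 10% in each arm | 50% | 37.8% | (0.30 − 0.05)/0.90 = 27.8% | 0.74 |
| 10% in each arm | 60% | 36.7% | (0.30 − 0.06)/0.90 = 26.7% | 0.73 |

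The first three rows move the RR toward 1, against IV iron. The last two move it away from 1, in favor of IV iron.

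**5. No true effect (39% in both arms), r = 60%.** Removing 15% oral and 5% IV gives 37.9%/35.3%, RR 1.07. Removing 5% oral and 10% IV gives 36.7%/37.9%, RR 0.97. A spurious difference can appear in either direction.

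**6. What each set removes.** Under the ITT set, only the dose condition can discard a known six-week value. The post-baseline assessment condition cannot, because the six-week hemoglobin is itself such an assessment. Under the Primary Analysis set, week-2 attendance is a further reason for removal. In both cases m is unknown before the trial.

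**The case against.** The strongest reply is that section 9.4 states the right principle and never assigns the Primary Analysis set to the log-binomial model. That the set carries the model is inferred from its name. This stands. If the ITT set is used, the week-2 condition falls away and only undosed women are lost, perhaps very few. The definition still contradicts the principle, and the text leaves two candidate sets for one analysis.

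A second reply is that few women would be removed. Section 4.10.6 requires tracking and a home visit within 48 hours of a missed appointment. The week-2 visit may take place at home and has a window of ±3 days, and section 4.10.4 allows unscheduled visits for lost tablets. These safeguards make a large share with a week-6 value but no week-2 visit less likely. They do not justify excluding those who remain.

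Three stronger readings are tempting, and the documents do not support them:

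- **That the exclusions flatter oral iron.** A reader might reason that an oral-arm woman who misses week 2 also misses resupply and is more often anemic. Removing 10% of both arms at the same 50–60% anemia rate pushes the RR the other way, to 0.73–0.74. The direction is open.
- **That power collapses to about 51–67%.** This needs removal from the oral arm only, together with 31.2% in the IV arm (a literal 20% reduction) in place of the stated 30%. At 30% the same oral-only removal gives 68–81%, and that too is only an illustration.
- **That the dose condition is plainly asymmetric.** Tablets go home with the woman, but section 4.10.2 lists giving study drug in either arm as an enrollment step, and Table 3 marks the control drug at baseline. Whether the first tablet is observed is not settled.

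A reader might also infer that early maternal deaths drop out of the ITT set. That depends on what counts as a relevant efficacy assessment for a mortality outcome, which the protocol does not say.

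**Conclusion.** The point holds. Sections 9.3 and 9.4 conflict, and under either candidate set randomized women with a known six-week hemoglobin can be excluded on post-randomization criteria. This follows from the text alone and needs no assumed number.

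The consequence is less certain. Equal removal unrelated to outcome causes no bias, and at an assumed 10% it costs about three points of power (91.9% to 89.0%), just under the 90% target. Bias arises only if removal is related to outcome, and its size and direction depend on how removal differs between arms, which the documents do not give. The reason to correct the text is that the primary comparison could lose the protection of randomization while being reported as intention to treat. It is not that a particular distortion has been shown.

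**What to change.** - Define ITT as all randomized women, analyzed by assigned arm, and drop the dose and post-baseline assessment conditions.
- State in section 9.4 that the primary log-binomial analysis uses every randomized woman with a six-week hemoglobin, regardless of dosing or week-2 attendance.
- Name a method for missing six-week hemoglobin, at least as a sensitivity analysis. One example is multiple imputation using arm, site and hemoglobin at other visits. If the statistical analysis plan already does this, refer to it.
- Keep the present Primary Analysis set only as a sensitivity set.
- Correct the circular Per Protocol definition to a subset of ITT.

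The cost is a rewording of sections 9.3 and 9.4 and, if adopted, one imputation model. No new data are needed. The change should be made before any comparison by arm, including the interim efficacy analysis, which can end the trial.

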4.10 VISIT SCHEDULES AND ASSESSMENTS

Participants will be seen at the postnatal wards between 6 and 48 hours after delivery at study sites for enrolment then at two, six and 12 weeks postpartum and at the end of study (EOS) visit at six months postpartum. Aside the baseline visits for enrolment, all other visits will be done at the participants' home or at the healthcare facility depending on the participants' preference.

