7.3.1 Safety issues with ferric carboxymaltose

7.3.1.1 Hypersensitivity reactions (HSRs)

Parenterally administered iron preparations including FCM can cause hypersensitivity reactions including serious and potentially fatal anaphylactic/anaphylactoid reactions (39). The risk is enhanced for patients with known allergies including druq allergies, patients with a history of severe asthma, eczema, or other atopic allergies. There is also an increased risk of hypersensitivity reactions in patients with immune or inflammatory conditions (e.g., systemic lupus erythematosus, rheumatoid arthritis). **These conditions with increased risk for HSRs are excluded from this study.**

Other risk factors for hypersensitivity reaction are previous reaction to intravenous iron, fast iron infusion rate and staff or patient anxiety.

- FCM should only be administered when study staff that are trained to evaluate and manage anaphylactic reactions are immediately available and, in an environment, where full resuscitation facilities can be assured.
- Each patient should be observed for adverse effects for at least 30 minutes following FCM administration. If hypersensitivity reactions or signs of intolerance occur during administration, the infusion must be stopped immediately, and the resuscitation protocol activated (*Refer to IVON Trial Protocol No: 02; Administration of Intravenous Ferric Carboxymaltose and the Emergency Treatment of Hypersensitivity Reaction Type 1 (Anaphylaxis).*
- Facilities for cardiorespiratory resuscitation and equipment for handling acute anaphylactic/anaphylactoid reactions should be available, including an injectable 1:1000 adrenaline solution. Additional treatment with antihistamines and/or corticosteroids should be given as appropriate.

CAUTION:

- Acute hypersensitivity reactions during iron infusions are very rare but can be life-threatening and so these special precautions must be always considered.
- Every administration of FCM:
 - Must be preceded by a recheck for risk factors for an HSR, the general condition of the patient and base-line observations including pulse rate, blood pressure and respiratory rate.
 - The infusion should be prepared as stated in the manufacturer's instructions.
 - Infusion should be initiated slowly and not increased until it is clear that it is being welltolerated (usually after 5-10 min).

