7.4 Data analysis plan for adverse events (Harm)

Using intention to treat analysis, the absolute risk, the frequency/incident rate and severity grade of anticipated adverse drug reactions such as abdominal pain, nausea and vomiting, hypotension and hypophosphatemia for participants in each study arm, the incident rate of any Serious Adverse Reactions (SAR) which are SAEs that are thought to be causally linked to the trial drug and Suspected Unexpected Serious Adverse Reaction (SUSAR) which are unexpected occurrence of a SAR for each arm of the study will be collated and analyzed. The mean and SDs or median and interquartile range for serum phosphate level will be calculated as appropriate, while extreme values will be stated if observed.

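### Safety set membership can depend on later contact in the oral arm only, and sections 7.4 and 9.3 name different populations for harms

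*Protocol*

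**What the plan says.** Protocol 9.3 lists the analysis populations. The Safety set is "all patients that received at least one dose of study drug and had at least one post-baseline safety assessment", and "Patients will be analyzed according to treatment received". The qualifying assessment is not defined further.

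The arms differ in what happens on the day of dosing. For ferric carboxymaltose (FCM), section 4.6.1 says "Thereafter, they will be observed closely for a minimum of 30 minutes after infusion", and 7.3.1.1 says "Each patient should be observed for adverse effects for at least 30 minutes following FCM administration". For ferrous sulphate, 4.6.1 says "The women randomized to the control arm (FS) will be given for take home", and no observation after a first tablet is described. In the enrolment steps of 4.10.2, the adverse event check is listed before study drug is given. Contacts after enrolment are scheduled alike in both arms: "then at two, six and 12 weeks postpartum and at the end of study (EOS) visit at six months postpartum" (4.10).

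The harms section does not use the Safety set. Section 7.4 opens: "Using intention to treat analysis, the absolute risk, the frequency/incident rate and severity grade of anticipated adverse drug reactions". The ITT set in 9.3 is "all randomized patients with at least one relevant post-baseline efficacy assessment, and who had at least one dose of study drug", analysed by assigned arm.

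**The concern.** A safety population should not select women on follow-up, and above all not in one arm only. Here an infused woman has a witnessed dose and an observation for adverse effects within the hour. She can therefore enter the Safety set even if nobody sees her again. She then sits in the denominator with no later event recordable. An oral-arm woman with no further contact leaves the denominator. For events that arise after discharge, this alone can separate the two rates when true risk and loss are equal.

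The other population named for harms has a different fault. Its efficacy condition treats the arms alike, but it can remove a woman with a day-0 infusion reaction, the event that the observation period exists to detect. Adverse drug events are a stated objective (2.2) and a secondary outcome (3.1.2), so their denominator should be settled.

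**Working it through.** **Inputs**
- 700 women per arm (4.3).
- x = share of each arm never contacted after enrolment. The protocol does not give it. I assume 2%, 5% and 10%; the upper end equals the overall loss allowance in 4.3.
- p = true risk of a post-discharge adverse event, equal in both arms. I assume 20%, with 5% as a check.
- The plan states no figure for the Safety set, so there is none to reproduce.

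**Rates under the Safety set on its natural reading, loss unrelated to harm**
- FCM: p(1 - x)n / n = p(1 - x)
- Oral: p(1 - x)n / ((1 - x)n) = p
- Apparent FCM/oral ratio: 1 - x

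Worked case, x = 5%, p = 20%: 35 women lost per arm, 665 still observed, 0.20 × 665 = 133 events in each arm. FCM 133/700 = 19.0%; oral 133/665 = 20.0%; ratio 0.95.

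| x | lost per arm | FCM rate | oral rate | ratio | chance of a falsely significant result favouring FCM |
|---|---|---|---|---|---|
| 2% | 14 | 19.6% | 20.0% | 0.98 | 3.8% |
| 5% | 35 | 19.0% | 20.0% | 0.95 | 6.8% |
| 10% | 70 | 18.0% | 20.0% | 0.90 | 15.1% |

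The last column uses an unpooled normal approximation at two-sided 0.05, so the nominal value in that direction is 2.5%. At p = 5% the three values are 3.1%, 4.0% and 6.3%.

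**Loss related to harm.** Keep p = 20% in retained women and in all FCM women, and give the lost oral women a higher risk q. True oral risk = 0.20(1 - x) + qx. The observed ratio remains 1 - x.
- x = 10%, q = 40%: true oral risk 0.18 + 0.04 = 0.22; true ratio 0.20/0.22 = 0.909; observed 0.900. The error nearly vanishes.
- x = 10%, q = 60%: true oral risk 0.18 + 0.06 = 0.24; true ratio 0.20/0.24 = 0.833; observed 0.900. The error now favours oral iron.

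**The ITT set of 9.3.** The observation after infusion is not an efficacy assessment, so a woman with no later efficacy assessment drops out in either arm. If her loss is unrelated to the reaction, the expected reaction rate is unchanged but her individual event disappears from the analysis. If a reaction makes loss more likely, the infusion-reaction rate is understated.

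**After the fix.** With all dosed or dispensed women in both denominators and equal loss, both rates are p(1 - x), for example 133/700 = 19.0% in each arm, and the ratio is 1.00 for every x.

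**The case against.** The strongest reply is that section 7.4 puts harms under intention to treat, and nothing in the protocol says that harm rates will be computed on the Safety set. That stands. A reader might infer that harm rates in this trial are tilted towards FCM, but the text does not establish it. What 7.4 does establish is a conflict with 9.3, and the ITT set defined there suits harms no better. If 7.4 means every randomised woman by assigned arm, it should say so, because that is not the set that 9.3 calls ITT.

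Second, the protocol never says that the infusion observation counts as the qualifying assessment. Table 3 places drug administration in the baseline column, and 7.1 speaks of assessment before dosing and at follow-up visits. Read as a follow-up-visit assessment, the condition would be the same in both arms. That reading is possible. But 7.3 counts any monitoring and recording of adverse events as safety assessment, and an observation for adverse effects after the dose fits that description, so the arm-dependent reading is the more natural one.

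Third, a reader might infer that an oral-arm woman is in the set only if she returns at week 2. The documents do not support this. Visits may be at home (4.10), a missed visit triggers tracking and a home visit (4.10.6), unscheduled contacts and volunteered events are recorded (4.10.4, 7.1), and any later visit also qualifies her. Only women never contacted again drop out, so x is probably well below 10%.

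Fourth, hypophosphatemia is a poor example of dilution. It is measured on visit samples, and nothing says that unsampled women are counted as normal.

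**Conclusion.** The point holds in a limited form. As 9.3 is written, Safety set membership can depend on follow-up in the oral arm and not in the FCM arm. In addition, 7.4 and 9.3 disagree on the population for harms and on grouping by assigned or received treatment, and the ITT set of 9.3 can lose day-0 infusion reactions.

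If the Safety set is used, the distortion in post-discharge events is a factor of 1 - x. That is 0.98 or 0.95 for 2% or 5% never contacted again; 0.90 would need the entire 10% allowance to be such women. These figures rest on four assumptions: that the infusion observation counts, that true risks are equal, that loss is equal, and that loss is unrelated to harm. A fixed bias in favour of FCM cannot be claimed, because loss caused by adverse events can cancel or reverse it. Day-0 reactions counted over all infused women are not diluted. The effect is modest, but the selection is avoidable.

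**What to change.** - In 9.3, define the Safety set identically for both arms: all randomised women who started the infusion or were dispensed ferrous sulphate, with no post-baseline assessment condition.
- Name this one population for harms in both 7.4 and 9.3, with one grouping rule.
- For harms measured at visits, such as hypophosphatemia, use the women assessed at that visit in each arm as denominator. This also avoids counting unobserved women as event-free.
- Report infusion-day reactions separately, over all women who started the infusion.

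The cost is a few sentences in two sections, settled before populations are assigned ahead of database lock. The small downside is that the oral denominator may include a few women who took no tablet. The change removes selection created by the definition. It does not correct for loss that truly differs between arms, so the number never contacted again should be reported by arm.
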